500-ml of normal saline (i.e. concentration of 1 μ g/ml) and enclosing the bag in an opaque sleeve. The placebo will be a 500-ml bag of normal saline (without active drug) also enclosed in an opaque sleeve. The infusion from this bag will be started at 30 ml/hour (corresponding to 30 μ g/hour) and run for at least 12 hours, unless adverse effects occur and the infusion is stopped prematurely (see titration protocol below). Vasoactive medications will be weaned as expeditiously as possible. When the donor is considered hemodynamically stable, initial transthoracic echocardiography (TTE) will be ordered and obtained as soon as possible. Repeat serum free T4 level should be drawn prior to organ recovery in both groups. Organ allocation will proceed per OPTN policy and routine allocation practices. All other aspects of donor management will also follow local OPO protocols.

Criteria for discontinuing or modifying allocated interventions {11b}

Titration protocol: T4 can be titrated down if:

- a) Systolic Blood Pressure above 180 mm Hg and increase of 30 mm Hg above baseline
- b) Heart rate over 120 bpm and increase by 20 bpm above baseline
- c) New tachyarrhythmia (atrial fibrillation, atrial flutter, supraventricular tachycardia, ventricular tachycardia) or new onset ectopy (ventricular premature contractions > 6/min)
- d) Other significant change, at discretion of the coordinator

The dose should be reduced in increments of 10 μ g/hour (i.e. to 20 then 10 μ g/hour). The infusion can be discontinued if hemodynamic instability persists despite weaning.

Open-label T4 can be given to the placebo group after 12-hours at the discretion of the managing team (whether for persistent hemodynamic instability, low EF on echo, or physician preference). T4 can also be continued beyond 12-hours of study infusion for the same reasons in the intervention group.

Strategies to improve adherence to interventions {11c}

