There will be a one-month run-in period at each site where screening logs will be checked by the site and central study coordinators for completeness and accuracy. They will review all cases where donors were not enrolled within 24 hours or if other reasons for ineligibility were provided and provide feedback. The site and study coordinators will have weekly conference calls for the first month (and then monthly thereafter) to discuss issues with adherence. They will also provide feedback to individual OPO personnel if study protocols are violated. The study statistician will perform monthly audits of study data for completeness.

Relevant concomitant care permitted or prohibited during the trial {11d}

All standard OPO donor management practices will be continued throughout the study period until and including organ allocation and recovery. The only intervention prohibited is administration of thyroid hormone to those donors allocated to the placebo group for the first 12 hours after randomization.

Provisions for post-trial care {30}

Data collection on non-human organ donors ends at time of organ procurement or end of donor management (for authorized brain-dead potential donors who do not go on to donate organs).

Outcomes {12}

The primary outcome for this study is the proportion of hearts transplanted (the number of hearts transplanted divided by the total number of potential donors – including those authorized but not recovered).

The primary safety outcome for this study is 30-day graft survival in those receiving hearts from those enrolled in this study. This is defined by patient survival with the originally transplanted heart and no mechanical circulatory support. It will be assessed primarily at 30-days but also at 1-year.

Secondary outcomes will include:

1. Time from randomization to weaning off vasopressors: defined as being off all vasoactive agents, except for vasopressin (≤ 1 U/hr)
2. Proportion weaned off vasopressors by 12-hours (same criteria as #1)
3. Vasopressor-inotrope score at 12-hours (excluding vasopressin ≤ 1 unit/hour)
4. Time achieving hemodynamic stability adequate to order first echocardiography
5. Ejection fraction measured on first donor echocardiography
6. Lungs and total thoracic organs transplanted
7. Total number of organs transplanted

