8. Additional outcomes routinely collected from heart transplant recipients will also be aggregated and analyzed, including need for post-transplant mechanical circulatory support and other measures of primary graft dysfunction

Safety endpoints:

The following adverse events will be prospectively collected on all study donors. All events deemed either related or potentially related to the study drug infusion will be reviewed by the site coordinator. Any serious related events (defined as hemodynamic instability leading to cardiac arrest or donor loss prior to organ recovery) will be forwarded to the DSMC for additional review:

1. Severe hypertension (systolic BP > 200 mm Hg)
2. Tachycardia (HR > 150 and increased more than 20 over baseline)
3. New/worsened tachyarrhythmia (SVT, Atrial fibrillation, Ventricular tachycardia or fibrillation)
4. Cardiac arrest or any donor loss prior to the OR
5. Fever – new, above 102 degrees Celsius
6. New skin rash

Participant timeline {13}

Sample size {14}

The proportion of potential heart donors who were able to provide a heart for transplantation in our pilot studies was between 30-60% (12, 14), a rate concordant with the recent literature (23). Proposed effect sizes of thyroid hormone treatment have ranged as high as an absolute increase of 20% or more in proportion of hearts transplanted in non-randomized studies (24); a large retrospective analysis of UNOS data found that those who received thyroid hormone (57% of 40,124 donors) had more hearts transplanted (7). The increase was from 25.8% without treatment to 35% with thyroid hormone (among all donors, not only those who were strictly heart-eligible, as required in this study). Based on our pilot data and this literature, we propose an absolute treatment effect size of 10% as the threshold for this study. In order to detect an increase in the proportion of hearts transplanted from 35% to 45%, we will need 752 total donors (376 per group), assuming 80% power and a one-sided alpha of 0.025. Because we expect some loss of donors after enrollment (e.g., clinical issues that interrupt adherence to the protocol), we will enroll a total of 800 donors (400 in each study group).

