[name]	Transplant Researcher and Statistician SRTR senior scientist	Professor of Surgery with tenure, Director of Clinical Research, SSM Health Saint Louis University Transplant Center
[name], MB,ChB, DA, FNCS	Medical director of organ procurement organization	Professor and Chief of Anesthesiology, Harborview Medical Center, University of Washington Medicine Medical Director, LifeCenter Northwest OPO
[name]	Medical Ethicist	Professor and Director, Albert Gnaegi Center for Health Care Ethics, Saint Louis University
[name], MS	Transplant Epidemiology and Statistical Analysis	Director, Scientific Registry of Transplant Recipients Director, Transplant Epidemiology, Hennepin Healthcare Research Institute

The DSMC statistician ([name]) will analyze the primary outcome and primary safety data at the time of the interim analysis. These results will be shared with the entire DSMC, who will discuss and provide a recommendation on whether to continue recruitment or whether to terminate the study. The DSMC members are independent from the study investigators and are not involved in the procedures of the study in other than this review and the review of any serious safety events.

Adverse event reporting and harms {22}

Study data forms include prospective ascertainment of adverse events entered by the organ procurement coordinators caring for each donor (events listed under *Outcomes, Safety Endpoints* and shown on forms provided in Appendix A). Any events deemed either related or potentially related to the study drug infusion will be reviewed by the site coordinator. The site coordinator will report all AEs that are unanticipated and/or serious to the central site, within 72 hours, for further review. This includes all cases of cardiac arrest or donor instability leading to loss of the donor prior to organ recovery. These events, with narrative review, will be forwarded to the DSMB for review within one week. Incidence of all AEs (by study group) will be provided to the DSMB monthly and also be analyzed as part of the interim safety analysis. In addition, outcomes in the recipients receiving hearts from study participants will be analyzed in the interim analysis to ensure non-inferior graft function and survival.

Frequency and plans for auditing trial conduct {23}

The study statistician (in consultation with the study coordinator and study PI) will audit data and conduct of the trial and oversee and feedback given to each site coordinator.

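### Donor adverse events go to the monitoring committee only as all-period incidence by study group; a 0–12 hour companion comparison is needed because T4 may be running in both arms after that

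*Combined protocol and SAP*

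**What the plan says.** **What is collected.** Outcomes {12}, under Safety endpoints, states: "The following adverse events will be prospectively collected on all study donors". The list covers severe hypertension, tachycardia, tachyarrhythmia, arrest or donor loss, fever and rash. It gives no start, stop or exposure rule. One item expressly runs past 12 hours: "Cardiac arrest or any donor loss prior to the OR".

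**What the committee sees.** Section {22} states: "Incidence of all AEs (by study group) will be provided to the DSMB monthly". The same figures also feed the safety review at the interim. Events that are unanticipated and/or serious go to the central site and on to the committee with a narrative.

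**How long donors are followed.** Section {30} states: "Data collection on non-human organ donors ends at time of organ procurement or end of donor management".

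**When the arms differ by design.** Section {11d} prohibits only "administration of thyroid hormone to those donors allocated to the placebo group for the first 12 hours after randomization". Section {11b} adds: "Open-label T4 can be given to the placebo group after 12-hours at the discretion of the managing team". For the other arm it says: "T4 can also be continued beyond 12-hours of study infusion for the same reasons in the intervention group". Section {17b} repeats that any participant may receive open-label T4 once the 12-hour study period ends.

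**What handles open-label T4.** Section {20a} plans a secondary analysis restricted to placebo donors without open-label T4, placed with the primary-outcome text. Section {20c} allows later analyses that exclude donors not managed to protocol. Neither is tied to donor adverse events.

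**The concern.** Read as written, the by-group incidence table combines two periods. In the first 12 hours the arms differ by design. Afterwards T4 may be running in either arm, and the table does not separate the two. If T4 causes hypertension, tachycardia or arrhythmia in a placebo donor at hour 15, the event is scored against placebo.

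Crossover is foreseeable. Section {11b} names persistent instability, low ejection fraction and physician preference as reasons for open-label T4. Section {6b} describes T4 as common practice at almost all procurement organizations, and care providers are unblinded.

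What is at stake is how a reassuring table should be read. Similar rates could mean that T4 adds little risk, or that many placebo donors also received it. For non-serious events, which need no narrative unless they are unanticipated, the by-group table is the main evidence the committee has.

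**Working it through.** **Inputs from the documents.** The interim analysis is at 376 donors, about 188 per arm at 1:1. Full enrolment is 400 per arm. The documents state no donor adverse event rate, no expected open-label share and no adverse event power, so there is no figure of the plan's own to reproduce on this point.

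**Assumed inputs (illustration only).**
- Event risk is 5% without T4 and 15% with it, an excess of 10 points.
- f is the share of placebo donors, and g the share of T4-arm donors, with T4 running after 12 hours.
- r is the share of the 10-point excess that this late exposure adds.
- Background events after 12 hours are left out.

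**Formulas.**
- Placebo risk = 5 + 10·f·r
- T4-arm risk = 15 + 10·g·r
- Difference = 10·[1 + r·(g − f)] points
- Power (unpooled normal, two-sided 0.05) = Φ( |p1 − p0| / √[p1(1−p1)/n + p0(1−p0)/n] − 1.96 )

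The plan specifies no such test for adverse events. Power is used here only as a scale for how visible a difference would be.

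**One row in full** (f = 0.20, g = 0, r = 1, n = 188). The placebo risk is 5 + 2 = 7%. The standard error is √[(0.1275 + 0.0651)/188] = 0.0320. Then 0.08/0.0320 = 2.50, and Φ(2.50 − 1.96) = 71%.

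| f (placebo) | g (T4 arm) | r | T4 vs placebo risk | Difference (points) | Ratio | Power, 188 per arm |
|---|---|---|---|---|---|---|
| 0 | 0 | – | 15 vs 5% | 10 | 3.0 | 91% |
| 20% | 0 | 1 | 15 vs 7% | 8 | 2.1 | 71% |
| 35% | 0 | 1 | 15 vs 8.5% | 6.5 | 1.8 | 50% |
| 50% | 0 | 1 | 15 vs 10% | 5 | 1.5 | 31% |
| 20% | 0 | 0.5 | 15 vs 6% | 9 | 2.5 | 82% |
| 35% | 0 | 0.5 | 15 vs 6.75% | 8.25 | 2.2 | 74% |
| 50% | 0 | 0.5 | 15 vs 7.5% | 7.5 | 2.0 | 64% |
| 50% | 35% | 1 | 18.5 vs 10% | 8.5 | 1.85 | 66% |
| 35% | 35% | 1 | 18.5 vs 8.5% | 10 | 2.2 | 82% |
| 20% | 35% | 1 | 18.5 vs 7% | 11.5 | 2.6 | 92% |

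At 400 per arm, the three rows with g = 0 and r = 1 give 95%, 82% and 57%, against more than 99% with no late T4.

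**Reading the table.** The difference in points shrinks only when f exceeds g. When f equals g it is unchanged, but the ratio and the power fall because both rates rise. When g exceeds f by enough, the difference widens. The factor (1 − f·r) describes the shrinkage only if no T4-arm donor continues T4, which {11b} does not require.

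**Other base rates.** With 10% vs 20%, f = 25%, g = 0 and r = 1, the difference is 20 − 12.5 = 7.5 points. Interim power (pooled variance) falls from 78% to 50%.

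**The case against.** The strongest points against are these.

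- **Comparison as randomized is legitimate.** All-period incidence by arm is a valid treatment-policy summary. This stands, and the table should be kept.
- **Dilution is not certain.** T4-arm donors may also continue T4, and with equal late use the difference in points does not move. This stands. A reader might infer that the present table must hide harm from T4. The documents do not support that, since they give no rates and no late-use share for either arm.
- **The gap may lie in missing pages.** The Appendix A forms are not in the available text, and the participant timeline in {13} is empty there. A window or an onset time could sit in either place. This stands as a limit on the claim. It does not change {22}, which reports by study group and states no window.
- **The committee has other information.** Serious or unanticipated events come with a narrative, so timing and exposure can be examined case by case. This stands for those events, but not for non-serious, anticipated hypertension or tachycardia.
- **The pilot is a weak guide.** Its T4 hypertension and tachycardia arose in donors off vasopressors, whereas this trial requires vasopressor or inotrope support. Nothing shows that those events were late. This stands, and no rate is taken from the pilot here.
- **A 12-hour cut has its own flaw.** The infusion starts after randomization and runs for at least 12 hours, so a cut at 12 hours from randomization leaves out some on-infusion events and later donor losses. This is decisive against replacing the main table. It does not count against adding a second one.

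**Conclusion.** The point holds as a gap in reporting. The committee's by-group table mixes a protected period with one in which either arm may be on T4, and no analysis in the available text separates them for donor adverse events. The rates can be drawn together if late T4 use is at least as common in the placebo arm as in the T4 arm. With equal use the effect is on the ratio alone, and with higher placebo use it is on the difference as well.

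The size cannot be established. In the assumed cases a true 10-point difference reads anywhere from 5 to 11.5 points. The direction depends on two shares that the documents do not give, and the whole effect depends on T4 actually causing these events.

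A reader might go further and conclude that the randomized all-period comparison is wrong, or that unequal time to procurement biases it. The first does not follow, for the reasons above. The second is possible, but nothing in the documents shows it. This is a cheap improvement to harm detection and not a fault in the trial's design.

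**What to change.** In {22}:

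1. Keep the incidence of all adverse events by randomized group over the whole donor period, including arrests and donor losses before the operating room.
2. Add, in the monthly, interim and final reports, a prespecified companion comparison by randomized group of events with onset in the first 12 hours after randomization. This matches the protected period in {11d}.
3. List later events by arm and by whether T4 was running at onset.
4. Record an onset time for each event, if the Appendix A form does not already do so.

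The cost is a few lines of wording, possibly one extra form field, and fewer events in the windowed table. Late on-infusion events fall outside that table but remain in items 1 and 3. No dose, treatment rule, sample size or primary analysis changes.
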